5.1 Summary of Study Design

Study I4V-MC-JAIA (JAIA) is a Phase 3, multicenter, randomized, double-blind, parallel-group, placebo-controlled, outpatient, 52-week study evaluating the efficacy and safety of baricitinib 4-mg and 2-mg in patients with systemic lupus erythematosus (SLE) receiving standard therapy. The study has a screening period followed by a 52-week double-blinded treatment period and a 4-week post-treatment follow-up period.

Patients will be randomized in a 1:1:1 ratio between baricitinib 4-mg, 2-mg, and placebo. Study treatment will be administered as 2-mg and 4-mg tablets once daily (QD). Patients with documented renal impairment (defined as screening estimated glomerular filtration rate [eGFR] ≥ 40 to < 60 mL/min/1.73 m²), who are randomized to active treatment (either to the baricitinib 4-mg arm or the baricitinib 2-mg arm) will receive a baricitinib 2-mg QD dose by the interactive web-response system (IWRS).

Investigators are encouraged to taper corticosteroids according to clinical practice with a goal of ≤ 7.5 mg/day by Week 40. A single corticosteroid burst is permitted for patients with increased disease activity early in the treatment period. Complete details of corticosteroid rules in relation to the clinical trial endpoints can be found in JAIA Protocol (b) Section 7.7.1.

Patients who were unable to attend Visit 16 within the original protocol-defined window (Week 52/Day 365 \pm 4 days) due to COVID-19 were permitted to delay completion of the Visit 16 by up to 1 month. Patients who complete treatment in this study through Visit 16 may be eligible to participate in a study extension, if enrollment criteria are met.

[figure not shown]

Figure JAIA.5.1.

Illustrates the study design.

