Protocol-defined visit windows are defined as ± 3 days for Visit 3 (Week 1) and ± 4 days, from Visit 4 (Week 4) until Visit 16 (Week 52). If there is data within the protocol-defined window, that data will be used in by-visit analyses. If a protocol-defined visit is missing, then the nearest unscheduled visit data that exists will be mapped to that visit and included in by-visit analyses. If 2 unscheduled visits are equidistant to a missing visit, the earlier unscheduled visit will be used.

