6.4.2 Handling of Dropouts or Missing Data

Depending on the estimand being addressed, different data cutoffs and imputation methods will be used to handle intercurrent events. [Table JAIA.6.5](#) and [Table JAIA.6.6](#) specify how data will be included and the associated imputation method for each analysis. Intercurrent events (ICEs) for Study JAIA include:

- Initiation/increase of prohibited medication
- Permanent study drug discontinuation (COVID or non-COVID reasons)
- Study discontinuation (COVID or non-COVID reasons)

- Intermittent missing visits or assessment (COVID or non-COVID reasons), and
- Temporary treatment interruptions due to COVID reasons.

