6.4.2.1 Non-responder Imputation (NRI)

The non-responder imputation (NRI) method may be used when the estimand of interest uses the composite strategy (EMA 2020) for handling intercurrent events. In this strategy, patients will be considered non-responders for the NRI analysis if they do not meet the clinical response criteria or have missing clinical response data (based on each set of [Table JAIA.6.5](#)) at the analysis time point.

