6.4.2.3 Modified Last Observation Carried Forward (mLOCF)

Modified last observation carried forward will be used to impute missing data for analyses implementing ANCOVA or Wilcoxon rank-sum in the PP datapoint sets ([Table JAIA.6.5](#)), unless otherwise specified. For patients who receive prohibited medication, the last nonmissing observation at or before prohibited use will be carried forward to subsequent time points for evaluation. For all other patients discontinuing from the study or permanently discontinuing the study treatment for any reason, the last nonmissing postbaseline observation on or before discontinuation will be carried forward to subsequent time points for evaluation. If a patient has a missing record that cannot be imputed by other means for a postbaseline visit, the last postbaseline record prior to the missed visit will be used for this postbaseline visit.

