6.4.2.4 Hybrid Imputation

Hybrid imputation will be conducted to adjust for the effect of missing data due to the COVID-19 pandemic on the clinical trial. Missing data due to the COVID-19 pandemic includes: 1) data collected during drug interruption due to COVID-19 while a patient is considered off-drug; or 2) data which were not collected due to the COVID-19 pandemic (that is, missing visit data, in part or in whole). For the selected binary and continuous endpoints (see [Table JAIA.6.6](#)), multiple imputation (MI) will be used for imputing data that is missing due to COVID-19 in the PPCV datapoint sets (see [Table JAIA.6.6](#), PPCV definition), whereas other missing data not due to COVID-19 will be imputed by NRI for the binary endpoints and by MMRM for the continuous endpoints.

This hybrid imputation procedure addresses the hybrid estimand assuming that the effects of treatments would be the same as the PP analysis, had patients not experienced any intercurrent

event related to COVID-19 (see Section 6.4.2). The algorithm for hybrid imputation on binary and continuous endpoints (see [Table JAIA.6.4](#)) is as follows:

1. Identify all missing data, either due to COVID-19 or otherwise. Note: data following ICEs described in Section 6.4.2, will be set to missing prior to Step 2. Any data after prohibited medication or treatment/study discontinuation due to non-COVID-19 reasons will be all considered as missing due to non-COVID-19 reasons.
2. Implement the MI via PROC MI FCS REG or PROC MI FCS LOGISTIC to impute all continuous or binary missing data, respectively with treatment arm and stratified variables as covariates and generate m imputed complete data sets.
3. For each of these m imputed complete data sets from Step 2, the imputed data for missing not due to COVID-19 (as in Step 1) will be set to missing and the imputation method specified in [Table JAIA.6.6](#) will be implemented. For all other data including imputed or observed will be used for the analysis or to derive the binary outcomes.
4. Single estimates will be combined using Rubin's rules (Rubin 1987) via PROC MIANALYZE.

The number of imputed data sets will be $m=25$ and a 6-digit initial seed value prespecified for each analysis as 123456.

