Abbreviations: ACR = American College of Rheumatology Damage Index; BILAG = British Isles Lupus Activity Group; BICLA = British Isles Lupus Assessment Group Based Composite Lupus Assessment; CLASI = Cutaneous Lupus Erythematosus Disease Area and Severity Index; CNS = Central Nervous System; EQ-5D-5L = European Quality of Life–5 Dimensions–5 Level; FACIT = Functional Assessment of Chronic Illness Therapy; LLDAS = Lupus Low Disease Activity State; MCS= Mental Component Score; NRS = Numeric Rating Scale; PCS= Physical Component Summary; PGA = Physician's Global Assessment of Disease Activity; SF-36 = Short Form 36; SFI = SLEDAI Flare Index; SLE = Systemic Lupus Erythematosus; SLICC = Systemic Lupus International Collaborating Clinics; SRI-4 = SLE Responder Index; SLEDAI-2K = Systemic Lupus Erythematosus Disease Activity Index 2000; UK = United Kingdom; US = United States; VAS = visual analogue scale; WPAI:Lupus = Work Productivity and Activity Impairment – Lupus.

Note: Additional supplemental and sensitivity analyses are described in Section 6.10.3.3.

The datapoint sets are defined to estimate the estimands in [Table JAIA.6.5](#). The mITT population will be included in the analysis according to the treatment they were randomized, unless otherwise specified in [Table JAIA.6.6](#).

Patients who are imputed as nonresponders due to a qualifying intercurrent event for binary categorical efficacy variables, will be defined as such from the time of qualifying event, plus 1 day, onward.

Table JAIA.6.5. Datapoint Sets for Use in Efficacy/Health Outcomes Analyses

Datapoint sets	Definition of Missing Data Due to ICEs	Estimand of Interest

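### Section 6.3 fills a missing scheduled visit from the nearest unscheduled visit with no maximum distance, so a missed Week 52 SRI-4 can be taken from a remote record instead of being handled as missing

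*SAP*

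**What the plan says.** Section 6.3 sets windows of 3 days either side of Week 1 and 4 days either side of Weeks 4 to 52, and uses in-window data first. If a scheduled visit is missing, "the nearest unscheduled visit data that exists will be mapped to that visit and included in by-visit analyses". The only further condition is that the earlier of two equidistant unscheduled visits is taken. Section 5.1 adds that patients who could not attend Week 52 in its window because of COVID-19 "were permitted to delay completion of the Visit 16 by up to 1 month".

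The handling of a missed visit is set elsewhere:

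- Section 6.4.2 lists among the intercurrent events "Intermittent missing visits or assessment (COVID or non-COVID reasons").
- Section 6.4.2.1 makes patients non-responders if they do not meet the criteria or "have missing clinical response data" at the analysis time point.
- Section 6.4.2.4 applies MI to "data which were not collected due to the COVID-19 pandemic (that is, missing visit data, in part or in whole").
- Section 6.10.3.3.1 runs the tipping-point analysis on patients without treatment failure whose Visit 16 data are missing.

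Table JAIA.6.4 limits carry-forward of SLEDAI-2K items, BILAG letter scores and PGA to 36 days, with an exception for a previous BILAG score of E. These rules generally require that the visit took place.

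**The concern.** NRI, COVID-19 MI and the tipping-point analysis all act only on a value that is missing at Week 52. A mapped value is not missing, so none of the three reaches it. Because Section 6.3 sets no distance, an old record can become the Week 52 outcome. Only unscheduled visits are eligible, so a distant one would be used even where the scheduled Week 48 visit is closer.

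The rule is also looser than the plan's own standard. A PGA more than 36 days old may not be carried to a Week 52 visit that the patient attended. A whole unscheduled record of any age may stand in for a Week 52 visit that the patient did not attend. What is at stake is whether the primary endpoint for these patients is a Week 52 outcome, or a missing one handled as prespecified.

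**Working it through.** **Who is exposed.** The patient must (a) miss Week 52, (b) have had no treatment discontinuation, study discontinuation or prohibited medication, and (c) have an unscheduled record with SLEDAI-2K, BILAG and PGA. The SAP gives no count for any of these. It also does not show whether unscheduled visits collect all three instruments.

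**Distance.** Week 52 is Day 365 (Section 5.1). A Week 20 record (Day 141) would be accepted from 365 - 141 = 224 days away. The 36-day limit reaches back only to Day 365 - 36 = 329. The Week 20 record is a literal illustration, not a documented case.

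**Planning figure.** Section 5.2 gives about 750 patients randomized 1:1:1 (250 per arm), 40% placebo response, a 17-point difference (so 57%), two-sided alpha 0.05 and power above 90%. The chi-square normal approximation gives 96.9%, so the stated figure reproduces. Nothing here disputes it.

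**Standard error of the difference.** sqrt((0.40 × 0.60 + 0.57 × 0.43) / 250) = sqrt(0.4851 / 250) = 0.0440, or 4.4 percentage points.

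**Shift relative to NRI.** Assume that a share m of each arm is mapped instead of counted as non-response, and that mapped patients respond at the planning rates. The shift is m × (57 - 40) points.

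| m (assumed) | Patients per arm | Shift (points) | In SE |
|---|---|---|---|
| 1% | 2.5 | 0.17 | 0.04 |
| 3% | 7.5 | 0.51 | 0.12 |

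**Bounding cases**, with an assumed 20-57% response among mapped values:

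- Relative to NRI, 3% mapped in one arm and 1% in the other: 0.03 × 57 - 0.01 × 20 = 1.51 points (0.34 SE), in either direction.
- Relative to MI at 40% and 57%, 3% mapped in each arm: the baricitinib arm moves from 0.03 × (20 - 57) = -1.11 to 0, and the placebo arm from 0.03 × (20 - 40) = -0.60 to 0.03 × (57 - 40) = +0.51. The difference moves from -1.62 to +0.60 points. If mapped patients respond at the imputed rates, it does not move at all.

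**Patients with an earlier event.** Section 6.10.1 says that patients imputed as non-responders for a qualifying event "will be defined as such from the time of qualifying event, plus 1 day, onward". This fixes status by calendar time, so it makes no difference whether mapping is run before or after. Table JAIA.6.5 removes post-event observations from PPCV and PP, and Step 1 of Section 6.4.2.4 adds: "Any data after prohibited medication or treatment/study discontinuation due to non-COVID-19 reasons will be all considered as missing". Two openings remain. For continuous endpoints, a pre-event unscheduled record could be mapped to a post-event visit and enter the model as observed. In PPCV, a visit inside an excluded COVID-19 interruption could be filled from a record outside it and so leave MI.

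**The case against.** Four arguments stand against this point.

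1. **The group is narrow and the effect small.** This stands. All three conditions above must hold, and the COVID-19 delay of Visit 16 shrinks the group further. The 1-3% and 20-57% inputs are assumptions. The 1.51-point case needs threefold unequal mapping between blinded arms together with opposite extremes of response. The -1.62 case needs mapped patients to reverse the planned effect.

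2. **Mapping does not contradict Section 6.4.2.** This is a fair reading. Assigning records to visits decides which visits are missing, and imputation acts on the rest. Section 6.4.2.3 fits that sequence, since it turns to the previous record "If a patient has a missing record that cannot be imputed by other means for a postbaseline visit". A reader might infer that listing missed visits as intercurrent events forbids mapping, but the text does not say so. The defect is the absent limit, not the mapping itself.

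3. **Discontinued patients are already covered.** This stands for binary endpoints in PPCV and PP. A reader might infer that mapping turns patients who discontinued or took prohibited medication back into responders in the primary analysis, or that the order of the rules decides their status. Section 6.10.1 and Table JAIA.6.5 do not support that.

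4. **A cap around Week 52 could admit off-treatment records.** This also stands. Study drug is last assigned at Week 48 (Section 5.3), and normal completion of treatment is not an intercurrent event. A symmetric 14-day cap alone could therefore take in follow-up records, and the wording must exclude them.

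None of this supplies a distance limit for a patient with no earlier event who misses Week 52. The PP and AC analyses do not test the rule either, because they use the same mapping.

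**Conclusion.** The concern holds in a limited form. Read as written, Section 6.3 lets an unscheduled record from any post-baseline date stand as the Week 52 SRI-4 of a patient with no earlier discontinuation or prohibited medication. That patient then falls outside NRI, COVID-19 MI and the tipping-point analysis. This is a stated rule that is looser than the plan's own 36-day limit, so it is more than a missing detail.

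The likely effect is small: about 0.2-0.5 points against a standard error of 4.4, assuming 1-3% mapped equally in each arm and response at the planning rates. It is smaller still if unscheduled visits seldom collect all three instruments. The order of mapping relative to the intercurrent-event rules is an open question only for continuous endpoints and for COVID-19 interruption periods in PPCV. The change is worth making because the rule feeds the primary analysis, not because a large bias has been shown.

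**What to change.** Add to Section 6.3:

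> For efficacy, a post-first-dose unscheduled visit is mapped to a missing scheduled visit only if that visit is the nearest scheduled visit and lies within a stated maximum distance (half the interval to the adjacent visit, i.e. 14 days for 4-weekly visits, and in no case beyond the 36 days used in Table JAIA.6.4). Each unscheduled visit is used once, and records from the post-treatment follow-up period are not mapped to Week 52. Visit 16 data obtained under the COVID-19 delay of up to 1 month are kept as Visit 16. Visits excluded by the datapoint set (Table JAIA.6.5), including COVID-19 interruption periods in PPCV and post-event visits for continuous endpoints, are not filled by mapping. Any visit left unmapped is missing and is handled as in Table JAIA.6.6.

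The 14 days follow from the spacing: Visit 4 (Week 4) to Visit 16 (Week 52) is 12 intervals over 48 weeks, or 28 days each if equal, and half of that is 14. Another stated cap of no more than 36 days would also close the gap.

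The cost is a short paragraph and one windowing step in programming. The downside is that a few more visits are handled as missing. The SAP does not show whether database lock is still ahead. If it has passed, report the number of Week 52 values filled by mapping in each arm, with a sensitivity analysis that treats them as missing.

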6.4 Analysis Methods

The family-wise type I error rate (FWER) will be controlled at a 0.05 significance level for primary and major secondary endpoints using a prespecified graphical procedure (see Section 6.6). Unless otherwise specified, all other hypothesis testing will be conducted at a nominal significance level of 0.05.

For assessments of the primary endpoint and other binary efficacy and health outcomes endpoints, the following will be provided unless otherwise specified:

- Observed percentage for each treatment group along with the corresponding 2-sided 95% confidence interval (CI)
- The difference in percentages and 95% CI using the Newcombe-Wilson method without continuity correction, used for descriptive purposes
- The p-value and 95% (unless otherwise specified) CI for the odds ratio from the logistic regression model, used for primary statistical inference. The model will include the following explanatory variables: treatment, baseline disease activity (total SLEDAI-2K <10; ≥ 10), baseline corticosteroid dose (<10 mg/day; ≥ 10 mg/day prednisone or equivalent) and region (North America, Central/South America/Mexico, Europe, Asia and Rest of World). A Firth penalized likelihood will be used (Firth 1993), and
- If deemed necessary, additional analyses of categorical efficacy variables will be conducted to address sparse data or small sample sizes. The Fisher's exact test will be utilized if necessary.

Treatment comparisons of continuous efficacy and health outcome variables, except for SLICC/ACR Damage Index, Patient's Global Impression of Change and Joint Stiffness Duration, will use a restricted maximum likelihood-based MMRM analysis. The model will include the following explanatory variables as fixed factors: treatment, baseline disease activity (total SLEDAI-2K <10; ≥ 10), baseline corticosteroid dose (<10 mg/day; ≥ 10 mg/day prednisone or equivalent), region (North America, Central/South America/Mexico, Europe, Asia and Rest of World), visit (as categorical variable), baseline value, treatment-by-visit interaction, and baseline value-by-visit interaction. The response variable will be change from baseline across postbaseline visits. Within-patient errors will be modeled using an unstructured covariance structure. If the model fails to converge, the following covariance structures will be implemented in the following order: heterogeneous Toeplitz, heterogeneous autoregressive (1) heterogeneous compound symmetry, and autoregressive. The least squares (LS mean) difference, standard error, p-value, and CIs will be reported. Type III tests for the LS means will be used for the statistical comparisons.

Treatment comparisons of SLICC/ACR Damage Index will be made using analysis of covariance (ANCOVA) with baseline value as covariate. For Patient's Global Impression of Change, the analysis of variance (ANOVA) will be applied. For both models, treatment, baseline disease activity (total SLEDAI-2K <10; ≥ 10), baseline corticosteroid dose (<10 mg/day; ≥ 10 mg/day prednisone or equivalent), and region (North America, Central/South America/Mexico, Europe,

Asia and Rest of World) will be included as the categorical factors. Type III tests for LS means will be used for statistical comparison between treatment groups. The LS mean difference, standard error, p-value, and 95% CI may also be reported.

Treatment comparisons for duration of joint stiffness will be analyzed using a nonparametric method using the Hodges-Lehmann estimator. For the comparison between each baricitinib group and placebo group, the median difference of change from baseline score and its 95% CI from the Hodges-Lehmann estimator will be presented. The p-value for the median difference of change from baseline will be calculated using the Wilcoxon rank-sum test. A 95% CI for the median change from baseline score within each treatment group will be calculated using distribution-free confidence limits.

Time to first flare analyses will be analyzed using a Cox proportional hazards model with treatment group, with disease activity (total SLEDAI-2K <10; \geq 10), baseline corticosteroid dose (<10 mg/day; \geq 10 mg/day prednisone or equivalent), and region (North America, Central/South America/Mexico, Europe, Asia and Rest of World) fitted as explanatory variables. Hazard ratios, median time to flare, 95% CI and p-values will be presented for treatment comparisons to placebo. Only if flares occurred during the flare exposure time period (defined below for each datapoint set, respectively) will be counted as an event. For severe SFI flare, only the eligible severe flares will be counted (See 6 criteria for identifying eligible severe SFI flares in [Appendix 5](#)). Patients who do not have an event during the flare exposure time period will be censored at the end of the flare exposure time. The flare exposure time varies with different datapoint sets ([Table JAIA.6.5](#)).

- For the PPCV datapoint set, while considering the treatment effect without potentially confounding influences of COVID-19, the flare exposure time is defined as the time after the date of the first dose of study drug to the prohibited medication start date, treatment discontinuation date, study discontinuation date or date of the Week 52 visit, whichever is earlier, and excluding the time period of treatment interruption due to COVID-19 from the interruption start date plus 20 days to the interruption end date plus 20 days, both inclusive, if the interruption duration is 20 days or more.
- For the PP datapoint set, which ignores treatment interruption due to COVID-19, the flare exposure time is defined as the time after the date of the first dose of investigational product to the prohibited medication start date, treatment discontinuation date, study discontinuation date or date of the Week 52 visit, whichever earlier.
- For the As Collected (AC) datapoint set, which considers all collected data, the flare exposure time is defined as the time after the date of the first dose of investigational product to the study discontinuation date or date of the Week 52 visit, whichever earlier.

The annualized flare rate will be calculated as the number of flares divided by the flare exposure time in days multiplied with 365.25, where the flare exposure time is defined above and varies with the different datapoint sets. The number of flares includes the flare events that happened during the flare exposure time period. All collected flares, including mild/moderate and severe flares will be considered eligible for the analysis.

For comparing the flare rate in the baricitinib treatment group versus the placebo, the negative binomial regression model will be applied. The response variable in the model will be the number of flares during the flare exposure time with baseline disease activity (total SLEDAI-2K <10; ≥ 10), baseline corticosteroid dose (<10mg/day; ≥ 10 mg/day prednisone or equivalent), region (North America, Central/South America/Mexico, Europe, Asia and Rest of World) as explanatory variables. The natural logarithm of the flare exposure time will be used as an offset variable in the model to adjust for patients having different exposure times. The estimated rate ratio and the corresponding 95% CI, as well as the 2-sided p-value will be presented. When the negative binomial regression does not converge or the parameters cannot be estimated, an exact Poisson regression will be applied to calculate the rate ratio, 95% CI and the p-value.

Fisher's exact test will be used for patient disposition, adverse events (AEs), discontinuations, and other categorical safety data for between-treatment group comparisons. Continuous vital signs, body weight, and other continuous safety variables including laboratory variables will be analyzed by ANCOVA with treatment and baseline value in the model. Shift tables for select categorical safety analyses (for example, "high" or "low" laboratory results) will also be produced.

For efficacy, if study drug is temporarily interrupted (suspended) during a treatment period due to non-COVID related interruptions, such as, AEs or abnormal laboratory measures, etc., the measurements taken during the temporary interruption will be included in the analysis. For COVID related interruptions, [Table JAIA.6.5](#) provides details of inclusion/exclusion in the different analysis.

For safety evaluations, if study drug is temporarily interrupted (suspended) during a treatment period due to either COVID or non-COVID related interruptions, the measurements taken during the temporary interruption will be included in the analysis.

Missing data methods for the above analysis methods are specified in Section [6.4.2](#).

